9.2 Serious adverse event reporting

9.2.1 Definition of SAE

A SAE is defined as any adverse event (appearance of (or worsening of any pre-existing) undesirable sign(s), symptom(s) or medical conditions(s)) which meets any one of the following criteria:

- is fatal or life-threatening
- results in persistent or significant disability/incapacity
- constitutes a congenital anomaly/birth defect
- requires inpatient hospitalization or prolongation of existing hospitalization, unless hospitalization is for:
 - routine treatment or monitoring of the studied indication, not associated with any deterioration in condition
 - elective or pre-planned treatment for a pre-existing condition (that is unrelated to the indication under study and has not worsened since the start of study drug)
 - treatment on an emergency outpatient basis for an event not fulfilling any of the definitions of a SAE given above and not resulting in hospital admission
 - social reasons and respite care in the absence of any deterioration in the subject's general condition
- is medically significant, e.g. defined as an event that jeopardizes the subject or may require medical or surgical intervention.

All malignant neoplasms will be assessed as serious under “medically significant” if other seriousness criteria are not met.

Life-threatening in the context of a SAE refers to a reaction in which the subject was at risk of death at the time of the reaction; it does not refer to a reaction that hypothetically might have caused death if it were more severe (see Annex IV, ICH-E2D Guideline).

Medical and scientific judgment should be exercised in deciding whether other situations should be considered serious reactions, such as important medical events that might not be immediately life threatening or result in death or hospitalization but might jeopardize the subject or might require intervention to prevent one of the other outcomes listed above. Examples of such events are intensive treatment in an emergency room or at home for allergic bronchospasm, blood dyscrasias or convulsions that do not result in hospitalization or development of dependency or abuse (see Annex IV, ICH-E2D Guideline).

Any suspected transmission via a medicinal product of an infectious agent is also considered a serious adverse reaction.

All AEs (serious and non-serious) are captured on the CRF; SAEs also require individual reporting to Novartis Drug Safety & Epidemiology (DS&E) as per [Section 9.2.2](#) (SAE reporting).

9.2.2 SAE reporting

To ensure subject safety, every SAE, regardless of causality, occurring after the subject has provided informed consent and until 30 days after the last IP administration, must be reported to Novartis **within 24 hours of learning of its occurrence** as described below. Any SAEs experienced after this period should only be reported to Novartis if the investigator suspects a causal relationship to study treatment.

All follow-up information for the SAE including information on complications, progression of the initial SAE and recurrent episodes must be reported as follow-up to the original episode within 24 hours of the Investigator receiving the follow-up information. An SAE occurring at a different time interval or otherwise considered completely unrelated to a previously reported one must be reported separately as a new event.

Follow-up information provided must describe whether the event has resolved or continues, if and how it was treated, whether the blind was broken or not (if applicable) and whether the subject continued or withdrew from study participation. Each re-occurrence, complication, or progression of the original event must be reported as a follow-up to that event regardless of when it occurs.

If the SAE is not previously documented in the IB or Package Insert (new occurrence) and is thought to be related to the study treatment a Drug Safety and Epidemiology Department associate may urgently require further information from the investigator for Health Authority reporting. Novartis may need to issue an IN to inform all investigators involved in any study with the same study treatment that this SAE has been reported. Suspected Unexpected Serious Adverse Reactions (SUSARs) will be collected and reported to the competent authorities and relevant ethics committees in accordance with EU Guidance 2011/C 172/01 or as per national regulatory requirements in participating countries.

Follow the detailed instructions outlined in the Site Operations Manual regarding the submission process for reporting SAEs to Novartis. **SAEs must be reported to Novartis within 24 hours** of the investigator learning of its occurrence/receiving follow-up information.

9.3 Liver safety monitoring

To ensure subject safety and enhance reliability in determining the hepatotoxic potential of an investigational drug, a standardized process for identification, monitoring and evaluation of liver events has to be followed.

The following two categories of abnormalities / adverse events have to be considered during the course of the study (irrespective of whether classified/reported as (S)AE):

- Liver laboratory triggers, which will require repeated assessments of the abnormal laboratory parameter
- Liver events, which will require close observation, follow-up monitoring, and completion of the standard base liver CRF pages

Refer to [Table 15-1-Appendix 1](#) for complete definitions of liver events.

Every liver event defined in [Table 15-1-Appendix 1](#) should be followed up by the investigator or designated personnel at the trial site, as summarized below. Additional details on actions required in case of liver events are outlined in [Table 15-2-Appendix 1](#).

- Repeating liver chemistry tests (ALT, AST, TBL, PT/INR, ALP and γ GT) to confirm elevation within 48-72 hours.

These liver chemistry repeats should always be performed using the central laboratory, with the results provided via the standard electronic transfer. If results will not be available from the central laboratory within 24 hours, then the repeats can also be performed at a local laboratory to monitor the safety of the subject. If a liver event is subsequently reported, any local liver chemistry tests previously conducted that are associated with this event should have results reported on the unscheduled local laboratory CRF.

If the initial elevation is confirmed, close observation of the subject will be initiated, including:

- Consideration of treatment interruption if deemed appropriate
- Discontinuation of the investigational drug (refer to [Section 7.2](#) (Discontinuation of study treatment), if appropriate
- Hospitalization of the subject if appropriate
- Causality assessment of the liver event
- Thorough follow-up of the liver event should include:
 - Repeating liver chemistry tests two or three times weekly. Testing should include ALT, AST, ALP, PT/INR, and gGT. If total bilirubin is elevated $> 2 \times$ ULN, fractionation into direct and indirect bilirubin is required. To rule out muscular origin of transaminase elevations, CPK should be measured along with liver chemistry tests. Frequency of retesting can decrease to once a week or less if abnormalities stabilize or the study drug has been discontinued and the subject is asymptomatic. Retesting should be continued up to resolution.
 - Obtaining a more detailed history of symptoms and prior or concurrent diseases.
 - Obtaining a history of concomitant drug use (including nonprescription medications and herbal and dietary supplement preparations), alcohol use, recreational drug use, and special diets.
 - Exclusion of underlying liver disease, as specified in [Table 5-3](#).
 - Imaging such as abdominal US, CT, or MRI, as appropriate
 - Obtaining a history of exposure to environmental chemical agents.
 - Considering gastroenterology or hepatology consultations.

All follow-up information, and the procedures performed must be recorded as appropriate in the CRF.

9.4 Reporting Medication errors including misuse/abuse

Medication errors are unintentional errors in the prescribing, dispensing, administration or monitoring of a medicine while under the control of a healthcare professional, patient/subject or consumer (EMA definition).

Misuse refers to situations where the medicinal product is intentionally and inappropriately used not in accordance with the protocol.

Abuse corresponds to the persistent or sporadic, intentional excessive use of a medicinal product, which is accompanied by harmful physical or psychological effects.

All study treatment errors and uses outside of what is foreseen in the protocol will be collected in the dose administration record (DAR) CRF. Study treatment errors are only to be reported to Novartis Drug Safety and Epidemiology department if the treatment error is associated with a SAE.

All instances of misuse or abuse must be documented in the adverse event (AE) CRF irrespective of the misuse/abuse being associated with an AE/SAE. In addition, all instances of misuse or abuse must be reported to Novartis Drug Safety and Epidemiology. As such, instances of misuse or abuse are also to be reported using the SAE form/CRF. [Table 9-1](#) summarizes the reporting requirements.

Table 9-1 Summary of reporting requirements for medication errors

Treatment error type	Document in Dose Administration (DAR) CRF	Document in AE CRF	Complete SAE form/CRF
Unintentional study treatment error	Yes	Only if associated with an AE	Only if associated with an SAE
Misuse/Abuse	Yes	Yes	Yes, even if not associated with a SAE

For more information on AE and SAE definition and reporting requirements, please see [Section 9.1](#) and [Section 9.2](#), respectively.

9.5 Pregnancy reporting

To ensure subject safety, each pregnancy occurring after signing the informed consent must be **reported to Novartis within 24 hours** of learning of its occurrence. The pregnancy should be followed up to determine outcome, including spontaneous or voluntary termination, details of the birth, and the presence or absence of any birth defects, congenital abnormalities, or maternal and/or newborn complications.

Pregnancy must be recorded on the Pharmacovigilance Pregnancy Form and reported by the investigator to the local Novartis Drug Safety and Epidemiology Department. Pregnancy follow-up should be recorded on the same form and should include an assessment of the possible relationship to the study treatment.

Any SAE experienced during the pregnancy and unrelated to the pregnancy must be reported on a SAE form.

The study drug must be discontinued, though the subject may stay in the study, if she wishes to do so. All assessments that are considered as a risk during pregnancy must not be performed. The subject may continue all other protocol assessments.

9.6 Prospective suicidality assessment

Not Applicable.

9.7 Early phase safety monitoring

The investigator will monitor adverse events in an ongoing manner and inform the Sponsor of any clinically relevant observations. Any required safety reviews will be made jointly between medically qualified personnel representing the Sponsor and investigator. Such evaluations may occur verbally, but the outcome and key discussion points will be summarized in writing (e-mail) and made available to both Sponsor and all investigator(s). Criteria pertaining to stopping the study/treatment or adapting the study design are presented above.

When two or more clinical site(s) are participating in the clinical study, the Sponsor will advise the investigator(s) at all sites in writing (e-mail) (and by telephone if possible) of any new, clinically relevant safety information reported from another site during the conduct of the study in a timely manner.

10 Data review and database management

10.1 Site monitoring

Before study initiation, at a site initiation visit or at an investigator's meeting, a Novartis representative will review the protocol and CRFs with the investigators and their staff. During the study Novartis employs several methods of ensuring protocol and GCP compliance and the quality/integrity of the sites' data. The monitor will visit the site to check the completeness of subject records, the accuracy of entries on the CRFs, the adherence to the protocol and to Good Clinical Practice, the progress of enrollment, and ensure that study drug is being stored, dispensed, and accounted for according to specifications. Key study personnel must be available to assist the monitor during these visits.

The investigator must maintain source documents for each subject in the study, consisting of case and visit notes (hospital or clinic medical records) containing demographic and medical information, laboratory data, electrocardiograms, and the results of any other tests or assessments. All information on CRF's must be traceable to these source documents in the subject's file. The investigator must also keep the original informed consent form signed by the subject (a signed copy is given to the subject).

The investigator must give the monitor access to all relevant source documents to confirm their consistency with the CRF entries. Novartis monitoring standards require full verification for the presence of informed consent, adherence to the eligibility criteria, documentation of SAEs, and the recording of data that will be used for all primary and safety variables. Additional checks of the consistency of the source data with the CRF's are performed according to the study-specific monitoring plan. No information in source documents about the identity of the subjects will be disclosed.

10.2 Data collection

Designated investigator staff will enter the data required by the protocol into the Electronic Case Report Forms using fully validated software that conforms to 21 CFR Part 11 requirements. Designated investigator site staff will not be given access to the EDC system until they have been trained. Automatic validation programs check for data discrepancies and, by generating appropriate error messages, allow the data to be confirmed or corrected before transfer of the data to Novartis. The investigator must certify that the data entered into the Electronic Case Report Forms are complete and accurate. After database lock, the investigator will receive a CD-ROM or paper copies of the subject data for archiving at the investigational site.

Data not requiring a separate written record will be defined in the Site Operations Manual and [Assessment schedule](#) and can be recorded directly on the CRF's. All other data captured for this study will have an external originating source (either written or electronic) with the CRF not being considered as source.

All data should be recorded, handled and stored in a way that allows its accurate reporting, interpretation and verification.

10.3 Database management and quality control

Novartis staff or designee review the data entered into the CRFs by investigational staff for completeness and accuracy and instruct the site personnel to make any required corrections or additions. Queries are sent to the investigational site using an electronic data query. Designated investigator site staff is required to respond to the query and confirm or correct the data.

Concomitant medications entered into the database will be coded using the WHO Drug Reference List, which employs the Anatomical Therapeutic Chemical classification system. Medical history/current medical conditions and adverse events will be coded using the Medical dictionary for regulatory activities (MedDRA) terminology.

Laboratory samples will be processed centrally and the results will be sent electronically to Novartis or designee.

Diary data will be entered into an electronic diary by the subject. The system will be supplied by a vendor(s), who will also manage the database. The database will be sent electronically to Novartis or designee.

Randomization codes and data about all study drug(s) dispensed to the subject and all dosage changes will be tracked using the Novartis IRT system. The system will be supplied by a vendor, who will also manage the database. The database will be sent electronically to Novartis or designee.

Each occurrence of a code break via IRT will be reported to the clinical team and monitor. The code break functionality will remain available until study shut down or upon request of Novartis.

The occurrence of any protocol deviations will be determined. After these actions have been completed and the database has been declared to be complete and accurate, it will be locked and the treatment codes will be unblinded and made available for data analysis.

Data quality processes and query generation and resolution procedures will be provided in vendors' manuals.

Corporate Confidential Information

10.4 Data Monitoring Committee

Not required

10.5 Adjudication Committee

Not required

11 Data analysis

The analysis will be conducted on all subject data at the time the trial ends. Any data analysis carried out independently by the investigator should be submitted to Novartis before publication or presentation.

11.1 Analysis sets

For all analysis sets, subjects will be analyzed according to the study treatment(s) received.

The safety analysis set will include all subjects that received any study drug.

The PK analysis set will include all subjects with at least one available valid (i.e. not flagged for exclusion) PK concentration measurement, who receive any study drug and no major protocol deviations with relevant impact on PK data.

The PD analysis set will include all subjects with available PD parameter data who received any study drug and experienced no major protocol deviations with relevant impact on PD data. Any PD data for the primary endpoint obtained within 6 hours after rescue medication use or within 7 days of systemic corticosteroid will be set to missing.

11.2 Subject demographics and other baseline characteristics

All data for background and demographic variables will be listed by treatment sequence and subject. Summary statistics will be provided for all subjects, as well as for each treatment sequence.

Relevant medical history, current medical conditions, results of laboratory screens, drug tests and any other relevant information will be listed by treatment sequence and subject.

11.3 Treatments

Data for study drug administration (rescue medication) and concomitant therapies will be listed by treatment sequence and subject.

11.4 Analysis of the primary variable(s)

11.4.1 Variable(s)

The primary variable is trough FEV₁ to assess the bronchodilator effect of orally inhaled indacaterol salts (maleate and acetate) in subjects with asthma compared with placebo. Trough FEV₁ is defined as the average of the FEV₁ measurements at 23 h 15 min and 23 h 45 min post dose.

11.4.2 Statistical model, hypothesis, and method of analysis

The following hypothesis will be tested for each of indacaterol salts (acetate and maleate) versus placebo separately:

- HA₁: Indacaterol acetate is different to placebo in terms of the trough FEV₁ after 14 days of treatment
- HA₂: Indacaterol maleate is different to placebo in terms of the trough FEV₁ after 14 days of treatment

The trough FEV₁ after 14 days of treatment will be analyzed using an analysis of variance (ANOVA) with treatment, period and sequence as fixed effects and subject nested within sequence will be included as a random effect. The Kenward-Roger approximation will be used to estimate denominator degrees of freedom.

The final model estimates will include the LS mean for each treatment (indacaterol acetate, maleate and placebo) together with standard error (SE), the adjusted mean difference between indacaterol salts (acetate and maleate) and placebo, and corresponding two-sided 95% confidence intervals and P-value for the differences (acetate vs placebo and maleate vs placebo) using placebo as reference treatment. Additionally as a secondary consideration, an estimate of the differences in trough FEV₁ between indacaterol acetate (test) and indacaterol maleate (reference) will be calculated together with the corresponding two sided 95% confidence intervals.

Trough FEV₁ will be listed by treatment sequence, subject and visit/time and descriptive summary statistics will be provided by treatment and visit/time. Summary statistics will include arithmetic mean, SD, CV (arithmetic), median, minimum and maximum.

Graphical methods will be employed to show mean and individual figures for trough FEV₁

No adjustments will be made for multiplicity because the objective is to prove that both formulations must be statistically significantly different from placebo each at 2 sided 5% level of significance.

11.4.3 Handling of missing values/censoring/discontinuations

Subjects withdrawn for any reasons other than safety and tolerability may be replaced on a case by case basis.

If one of the 23h 15 min and 23h 45 min values are missing (or set to missing) then the remaining non-missing value will be taken as trough FEV₁. If both values are missing, or if the subject withdrew from the study, regardless of the reason for discontinuation, then trough FEV₁ will be regarded as missing.

If any of the values used in the trough FEV₁ are collected within six hours of rescue medication then the individual FEV₁ value will be set to missing and the imputation rules stated above will then be applied.

11.4.4 Summary statistics of safety

Not applicable

11.4.5 Summary statistics of pharmacokinetics

Not Applicable

11.4.6 Sensitivity analyses

Not Applicable

11.5 Analysis of secondary variable(s)

11.5.1 Efficacy / Pharmacodynamics

FEV₁, FEV₁% predicted, FVC, FVC% predicted, FEF_{25-75%} after 14 days of treatment will be analyzed using the same model as for the primary analysis with the additional fixed effects for time and treatment by time interaction term. Time will be repeated within each subject*period interaction term. An unstructured covariance matrix will be applied.

Peak FEV₁ (maximum FEV₁ post treatment) and Standardized FEV₁ AUC0-4h between screening (pre dose) and 4h post dose on Day 14 of treatment will be analyzed using the same model as for the primary analysis.

All subjects will be instructed to record PEF twice daily using a Peak Flow Meter device, once in the morning and once approximately 12 h later in the evening from screening and throughout the study. The morning/evening and the overall PEF (L/min) will be averaged between days 8 to 14 of each treatment period for each subject. Mean morning/evening and overall PEF will be analyzed using the same model as for the primary analysis and summarized by treatment.

Time to peak FEV₁ on Day 14 will be analyzed using non-parametric methods. The median difference and the two sided 95% confidence interval of the median difference in time to peak FEV₁ will be estimated using Hodges-Lehmann estimation procedure.

The number of puffs of the rescue medication use is recorded twice (morning/evening) by subjects in the eDairy. The average number of puffs of rescue medication use will be calculated as the number of puff >0 divided by days (14-8) for morning/evening and overall number of puffs of each treatment period for each subject and will be used for statistical analysis. The mean morning/evening and overall number of puffs of rescue medication use will be analyzed using the same model as for the primary analysis and summarized by treatment. The number and percentage of subjects with rescue medications, together with the number of events, were tabulated by treatment.

All the above secondary variables will be listed by treatment sequence, subject and visit/time and descriptive summary statistics will be provided by treatment and visit/time. Summary statistics will include arithmetic mean, SD, CV (arithmetic), median, minimum and maximum.

Graphical methods will be employed to show mean and individual figures for all parameters.

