6.1.3.1 Model checking procedures

Subjects withdrawn for any reasons other than safety and tolerability may be replaced on a case by case basis.

If one of the 23h 15 min and 23h 45 min values are missing (or set to missing) then the remaining non-missing value will be taken as trough FEV1. If both values are missing, or if the subject withdrew from the study, regardless of the reason for discontinuation, then trough FEV1 will be regarded as missing.

If any of the values used in the trough FEV1 are collected within six hours of rescue medication or 7 days of systemic corticosteroid then the individual FEV1 within 6 hours after rescue medication use or within 7 days of systemic corticosteroid will be set to missing. If rescue medication is taken during the 24 hour spirometry assessments then from the time of the rescue medication intake, all post-time point spirometry assessments will be considered as missing in this treatment period.

Subgroup analysis:

The primary analysis will be performed by subgroup of patients based on their compliance of study medication within the 7 days before the spirometry assessment: if spirometry assessment is done during day 14, then compliance will be calculated between day 8 and day 14 on a total number of 7 doses.

This analysis will be provided per compliance of study medication within the 7 days before spirometry assessment defined as follows:

- <80% Compliance of study medication within the 7 days before spirometry assessment (less than a total number of 5 doses)
- 80-100% Compliance of study medication within the 7 days before spirometry assessment (more or equal a total number of 5 doses)

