The number of puffs of rescue medication taken is recorded twice (morning/evening) by subjects in the eDiary. The morning/evening and overall (both morning and evening) number of puffs of rescue medication will be averaged separately between days 8 to 14 of each treatment period and each subject.

Below is an example for averaging the rescue medication for each treatment period and subject.

Subject	Day	Rescue Medication		
		Morning	Evening	Overall
5101	8	7	5	12
5101	9	6	8	14
5101	10	5	6	11
5101	11	6	7	13
5101	12	4	8	12
5101	13	9	6	15
5101	14	4	4	8

Corporate Confidential Information

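### The protocol's divisor for mean rescue use, read literally, is 6 days, while the Day 8 to 14 window has 7; one SAP line should settle the divisor

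*Protocol*

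**What the plan says.** Protocol 11.5.1 states that average rescue use "will be calculated as the number of puff >0 divided by days (14-8) for morning/evening and overall number of puffs". That sentence does not name the days over which the puffs are summed, and Protocol 2.2 gives no day window for the rescue endpoint either. For the other diary variable, the same section does name them: "The morning/evening and the overall PEF (L/min) will be averaged between days 8 to 14 of each treatment period for each subject".

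SAP 6.2.1 drops the bracketed divisor and says that the "number of puffs of rescue medication will be averaged separately between days 8 to 14 of each treatment period and each subject". It then announces an example ("Below is an example for averaging the rescue medication for each treatment period and subject") with one row for each of Days 8 to 14. The resulting averages are not visible, and redacted material follows the table directly.

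SAP 6.1.3.1 counts the same window when it defines compliance: "then compliance will be calculated between day 8 and day 14 on a total number of 7 doses".

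On the analysis, Protocol 11.5.1 says: "The mean morning/evening and overall number of puffs of rescue medication use will be analyzed using the same model as for the primary analysis". SAP 6.2.3 uses the same model.

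**The concern.** The protocol gives an explicit formula whose divisor is one day short of the window used everywhere else. The SAP implies a different divisor without stating it, and its visible text does not withdraw the protocol formula. Two analysts working from the two documents could therefore report different values for the same secondary endpoint.

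The endpoint is expressed in puffs, a scale that readers interpret directly, so a wrong divisor misstates the size of the treatment effect even where significance is untouched. A fixed divisor also takes no account of missing diary days.

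The phrase about puffs above zero adds a smaller ambiguity. It could mean the sum of puffs, which the filter leaves unchanged, or a count of entries above zero, which would be a different variable.

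**Working it through.** **Inputs.** The divisor is 14 − 8 (Protocol 11.5.1). The window is Days 8 to 14 (the PEF sentence in Protocol 11.5.1, and SAP 6.2.1). The data are the seven rows of the SAP 6.2.1 example.

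**Day count.** The literal divisor is 14 − 8 = 6. The inclusive count is 14 − 8 + 1 = 7, which agrees with the seven rows and the seven doses in the SAP. The ratio is 7/6 = 1.167.

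**SAP example.**
- Morning: 7 + 6 + 5 + 6 + 4 + 9 + 4 = 41
- Evening: 5 + 8 + 6 + 7 + 8 + 6 + 4 = 44
- Overall: 12 + 14 + 11 + 13 + 12 + 15 + 8 = 85 (= 41 + 44)

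| | Total | Divided by 7 | Divided by 6 | Excess |
|---|---|---|---|---|
| Morning | 41 | 5.86 | 6.83 | 16.7% |
| Evening | 44 | 6.29 | 7.33 | 16.7% |
| Overall | 85 | 12.14 | 14.17 | 16.7% |

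**Effect on inference, complete diaries.** The model is linear. Replacing 7 by 6 multiplies every subject-period value by 7/6, and so every LS mean, difference, standard error and confidence limit. The factor cancels in t = difference / SE and in any ratio of treatment means. Simulated paired data for 42 subjects showed the same: the difference was −0.459 with divisor 7 and −0.536 with divisor 6, with t = −5.97 and the same p-value both times.

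**Effect with incomplete diaries.** Suppose k days are recorded with total S. The mean per recorded day is S/k, and the fixed divisor gives S/6. The relative error is k/6 − 1:

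| Recorded days k | Error with divisor 6 |
|---|---|
| 7 | +16.7% |
| 6 | 0% |
| 5 | −16.7% |
| 4 | −33.3% |

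The error then differs between subject-periods, so it is no longer a common rescaling. It could differ by treatment if diary completeness does.

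**Could 6 be right?** Only with a six-day numerator. On the example this gives 77/6 = 12.83 for Days 8 to 13, 73/6 = 12.17 for Days 9 to 14, and 74/6 = 12.33 from the evening of Day 8 to the morning of Day 14. Neither document states such a window.

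**The case against.** The best counter-argument is that the bracket was never meant as a subtraction. It follows the word for days and could be loose shorthand for the Day 8 to 14 window, in which case the divisor is 7 and only the wording is at fault. This cannot be ruled out. Against it, the protocol writes day windows in ascending order elsewhere (Sections 2.2, 3.1 and 5.3, and the PEF sentence in 11.5.1), whereas here the larger number comes first, directly after the instruction to divide. Even as shorthand, a formula that yields 6 or 7 depending on the reader needs settling.

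Second, the SAP largely handles the point. The ordinary average of seven daily rows divides by seven, and a programmer working from the SAP would probably do that. This stands. A reader might infer that the trial's reported rescue results will be 17% too high. The documents do not support that, because the inflation arises only if the literal protocol formula is used instead of the SAP's average.

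Third, the redaction after the SAP table may hide the resulting means, so their absence should not be held against the SAP.

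Fourth, a reader might infer that incomplete diaries are always biased low under the protocol formula. They are not: the mean per recorded day is exact at six days and low only at five or fewer.

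Finally, the reach is limited. The sample size in Protocol 11.7 rests on trough FEV1, and the rescue-use withdrawal criterion in Protocol 7.2 works on daily inhalation counts, not on this mean.

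**Conclusion.** The point holds in a conditional form. The divisor in Protocol 11.5.1, taken literally, is 6 and does not match the seven-day window in the rest of the plan. The size is 16.7% on means, differences and confidence limits. That figure rests on three assumptions: the bracket is a subtraction, the numerator is the Day 8 to 14 total (taken from the PEF sentence and the SAP, since the rescue sentence names no window), and all seven diary days are recorded. Under those assumptions, significance and between-treatment ratios are unaffected. With missing diary days, the error runs from zero at six recorded days to increasingly negative values below that.

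This is a formula error, or at least an ambiguity, in a secondary endpoint. It has no bearing on the primary analysis. It merits correction because the two documents disagree and the visible text does not say which governs.

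**What to change.** Add one line to SAP 6.2.1, recorded as a correction to the formula in Protocol 11.5.1: for each subject and period, average rescue use is the sum of puffs on Days 8 to 14 divided by the number of those days with a diary entry (7 when complete), with zero-puff days counted in the divisor. Apply the same rule to the morning, evening and overall values. This settles the divisor, the numerator window, the meaning of the puffs-above-zero phrase and the handling of missing days together.

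If the averages are not already in the redacted text, print them under the example: 5.86 morning, 6.29 evening and 12.14 overall.

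The cost is one SAP line before database lock, with no new data and no change to the model. Changing the protocol text itself would need a written amendment under Protocol 13.1; the SAP line is the cheaper route and is enough to fix the calculation.
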